For this study, we will gather and analyze data on changes in body weight over a 6-month interval, roughly the time frame for a clinical trial, for individuals aged 12 and over to focus on age groups that are likely to be recruited in hyperphagia trials. It has previously been shown that weight changes in PWS may depend on age- and nutritional stages (Miller et al 2011), however, larger datasets across different age groups, with frequent measurements, are required to fully understand real world data regarding weight gain and obesity in PWS.

Weight may also be influenced by living situation, diet, medication and access to food. Therefore, we will also survey participants on diet and medication changes and food access, and study the extent to which these may play a role in any observed weight change.

Participants will be recruited from the U.S. and Canada through patient advocacy websites, Facebook and email. Interested participants will sign an informed consent prior to enrolling in the study.

III. Study Design

- We will utilize a commercially available text messaging based clinical app called Mosio (HIPAA and CFR Part 11 compliant) to collect data. (www.mosio.com)
- We will recruit up to n=300 participants. We expect to be able to recruit this number over 1-2 months prior to data collection (6 months).
- The study is expected to last 9 months, with 2 months for recruitment and start up, and 7 months for data collection.
- Mosio will create "Storylines"- a series of questions/surveys, that will be sent at pre-scheduled intervals, as and when participants sign-up.

Data to be collected:

1. Initial Survey at baseline only

- Was PWS diagnosis made by blood test.
- Gender
- Age
- Does the person receive growth hormone (GH) therapy? If yes, what age was therapy initiated? If no, were they ever on GH therapy? Age at initiation and how long were they on it.

- In the past 6 months, approximately how often did you weigh your child with PWS?
daily, weekly, monthly, less than monthly, only at doctor visits.
2. **Weight**- Once a week, every week, for 6 months. Participants will be sent a pre-scheduled text message reminder to weigh in and send a text response with the participant's weight.
 3. **Survey**-At 3 months and 6 months participants will answer a survey-
 1. Has there been any change in the living situation for the person with PWS in the last 3 months (example: moved, change in primary caregiver, illness in the family etc.? Y/N

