 2. To your knowledge has access to food at home or outside the home increased/decreased/stayed the same for the person with PWS?
 3. Has the activity level in the last 3 months increased/decreased/stayed the same for the person with PWS?
 4. Has there been medication change in the last 3 months for the person with PWS? Y/N
If yes-
Please list drug- and select start/stop/increased dose/decreased dose. Will provide option to list more than one drug.
 5. Please record participant's height.

Data will be stored in a secure database. Researcher will be given a log-in and have access to patient data throughout the course of the study.

IV. Duration of study

Study is expected to last 9 months with 3 months for recruitment followed by 6 months of data collection.

V. Eligibility and Recruitment of Participants

a. Inclusion Criteria

Male and female individuals diagnosed with PWS, 12 years and older.

b. Exclusion Criteria

- younger than 12
- non-PWS

c. Sample Size

Target sample size is 300 participants for this study

d. Recruitment of Participants

Participants will be informed of the study via website and social media outlets. These include patient advocacy websites, email, and the Global PWS Registry.

VI. Process of Obtaining Consent

Submission of information by participant or their representative: Participants will be provided details about the study, which will be posted on patient advocacy websites, Facebook, email and other social media outlets. They will be provided contact information and given every opportunity to read, understand and ask questions about the study via electronic means or phone. A consent form will be created on SurveyMonkey and a link to the consent form will be included with recruitment materials.

If they wish to participate in the study, participants or their parent/representative will be directed to an electronic informed consent form where they will be asked to review and sign an informed consent. Individuals providing consent will be asked to confirm that s/he is the participant or legally authorized representative of the participant. Consent from a legally authorized representative is required for participants who are minors or who are over the age of 18 but unable to provide informed consent. Because individuals with PWS have some degree of intellectual disability, the ability to provide consent will depend on the cognitive ability of the individual.

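### Apart from growth hormone history, no change made shortly before sign-up is recorded, so a 'no' at month 3 cannot separate stable from recently changed participants

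*Protocol*

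**What the plan says.** Protocol section III (Data to be collected) has two questionnaires.

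- **Item 1** is headed "Initial Survey at baseline only". It covers how PWS was diagnosed, gender, age, growth hormone history and how often the person was weighed in the past 6 months. The growth hormone items are "Does the person receive growth hormone (GH) therapy? If yes, what age was therapy initiated" and, for those not on it now, "If no, were they ever on GH therapy? Age at initiation and how long were they on it".
- **Item 3** sets the timing of the change questions: "At 3 months and 6 months participants will answer a survey". Question 1 reads "Has there been any change in the living situation for the person with PWS in the last 3 months", question 3 "Has the activity level in the last 3 months increased/decreased/stayed the same for the person with PWS" and question 4 "Has there been medication change in the last 3 months for the person with PWS? Y/N". A yes to question 4 leads to the drug and the direction of change, but no date is asked. Question 2, on food access, states no look-back: "To your knowledge has access to food at home or outside the home increased/decreased/stayed the same for the person with PWS".

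Weight is reported weekly for 6 months from sign-up. Section V admits anyone with PWS aged 12 or over and requires no period of stable treatment or living situation. Objective 2 in section I makes the study of factors affecting weight a primary objective. Section VII, item 2 plans a description of food access, living situation, activity and medication as such factors.

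**The concern.** To describe what part a factor played in weight change over a quarter, one needs to know what changed during that quarter and also what changed just before it, because weight may go on responding for some weeks. For months 3 to 6 the month-3 survey supplies that earlier quarter. For months 0 to 3 no survey does.

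A family that moved, or started a drug other than growth hormone, two weeks before sign-up answers 'no' truthfully at month 3. Nothing in the data tells that participant apart from one whose circumstances were stable. Any continuing effect of the earlier change then appears as weight change without a recorded cause. An analysis plan cannot repair this, because the information is never collected. What is at stake is the factor description for the first half of follow-up.

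**Working it through.** **1. Period covered by each question**

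| Topic | Initial Survey | Month-3 survey | Month-6 survey | Months −3 to 0 |
|---|---|---|---|---|
| Living situation, caregiver | not asked | months 0–3 | months 3–6 | not covered |
| Activity | not asked | months 0–3 | months 3–6 | not covered |
| Medication other than growth hormone | not asked | months 0–3 | months 3–6 | not covered |
| Growth hormone | current or past use, age at start; duration for past users | changes in months 0–3 | changes in months 3–6 | start or stop visible coarsely; dose change not |
| Food access | not asked | no window stated | no window stated | not assured |

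The gap follows from the wording alone and needs no assumption.

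**2. How many 'no' answers could hide a recent change**

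The only input from the protocol is the target sample size, N = 300 (section V.c). It is given without inputs, so there is no stated calculation to reproduce, and the point does not depend on it. Assume that a share r of participants has a given kind of change in any 3-month window, independently between windows. The protocol gives no r.

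- 'No' at month 3: N × (1 − r)
- Of these, changed in the 3 months before sign-up: N × r × (1 − r)

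| r (assumed) | 'No' at month 3 | of whom recently changed |
|---|---|---|
| 5% | 285 | 14 |
| 10% | 270 | 27 |
| 20% | 240 | 48 |
| 30% | 210 | 63 |

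**3. Effect on the mean of the 'no' group in months 0–3**

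Let e be the full effect of a change on weight and c the part of it that falls in months 0–3. The mean shifts by c × r × e.

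If changes are spread evenly over the quarter before sign-up and the effect builds linearly over 3 months, a change u months before sign-up has 1 − u/3 of its effect still to come. Averaged over u from 0 to 3, this gives c = 1/2. The shift is then 2.5%, 5%, 10% or 15% of e for r = 5%, 10%, 20% or 30%. For an assumed e of 3 kg and r = 10%, 20% or 30%, it is 0.15, 0.30 or 0.45 kg.

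These figures give every change the same sign. The survey itself allows starts and stops, and increases and decreases. Opposite effects would partly cancel in the mean and appear as unexplained spread, so the figures are upper cases for the assumed r, c and e.

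**4. Effect on a changed-versus-unchanged contrast, if one is made**

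Bias = c × e × [P(earlier change | changed in months 0–3) − P(earlier change | not changed in months 0–3)].

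- Independent quarters: both probabilities equal r, so the bias is zero on average.
- Linked quarters: the bias takes the sign of the difference. In an extreme negative link, with share 0 among the changed and r among the unchanged, the contrast is understated by c × r × e. With c = 1/2 that is 5% of e at r = 10% and 15% at r = 30%.

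The documents say nothing on whether changes cluster in time.

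**The case against.** Several stronger readings are tempting, and the protocol does not support them.

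- **A reader might infer that no drug change before sign-up is ever recorded.** The Initial Survey takes current or past growth hormone use, age at start and, for past users, duration. A recent start or stop of the one drug the protocol names can be seen, if coarsely. The gap concerns other drugs, and growth hormone dose changes.
- **A reader might infer that such participants will be counted as an unchanged reference group.** Section VII plans trends and a description of factors. It fixes no changed and unchanged groups and no estimate of an undisturbed course. Such a grouping could be set in an analysis plan, which is not at hand.
- **A reader might infer that the main weight trend is biased.** Objective 1 is a real-world description. People with recent changes belong to that population, and failing to label them does not move the overall trend.
- **A reader might suppose that families join because something has just changed.** Nothing in the recruitment text supports this.
- **A reader might take the kilogram figures as an estimate.** They rest wholly on assumed inputs and same-direction effects.

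These limits all stand. They leave the data gap itself intact: however the answers are later grouped, a 'no' at month 3 covers both stable and recently changed participants.

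**Conclusion.** The point holds in a limited form. By design, a change in home, caregiver, activity or a non-growth-hormone drug shortly before sign-up is not captured, and no later analysis can recover it. This weakens the description of factors for months 0 to 3, which serves a stated primary objective.

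The size is unknown. The counts of 14 of 285 to 63 of 210 rest on an assumed change rate of 5% to 30% per quarter, independence between quarters and full recruitment of 300. Bias in a changed-versus-unchanged contrast needs linked changes as well as a continuing effect. This is a cheap improvement to data collection and not a flaw that undermines the study.

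**What to change.** 1. In section III, send survey questions 1 to 4 at baseline as well, worded for the 3 months before sign-up. This also gives the food-access question an explicit window at that time point. Coverage then runs from month −3 to month 6.
2. In section VII, describe weight change in months 0 to 3 by pre-entry change status as well as by change during the quarter.
3. As a sensitivity analysis only, repeat the description in participants with no change in either quarter. It should not become the required definition of unchanged, because the group shrinks quickly.

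**Cost.** Four existing questions are sent once more through an automated system that already issues surveys at sign-up. Sign-up takes slightly longer and the answers carry recall error, though the Initial Survey already accepts a 6-month recall for weighing frequency.

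The sensitivity group is smaller. Assuming four independent items and independent quarters, at 10% change per item per quarter it falls from 0.9^4 = 66% (197 of 300) to 0.9^8 = 43% (129). At 20% it falls from 0.8^4 = 41% (123) to 0.8^8 = 17% (50).

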Protocol Title **A study to assess change in weight over six months in Prader-Willi Syndrome**

Date **February 22, 2018**

Principal Investigator [name].
Director of Research Programs
Foundation for Prader-Willi Research
[contact]
[contact]

Co-Investigators [name].
Associate Director of Translational Research Programs
Foundation for Prader-Willi Research
[contact]
[contact]

[name].
Associate Director of Research Programs
Foundation for Prader-Willi Research
[contact]
[contact]

Sponsor Name Foundation for Prader-Willi Research (FPWR)
[name]
[name]

Sponsor Study Number 2018_01

Confidentiality Statement: Information contained within this document is not to be disclosed in any way without the prior permission of the Principal Investigator.

I. Objectives

The primary objectives of the study are:

1. Perform a real-world study of weight changes over 6 months in PWS children and adults aged 12 and over.
2. Study factors that could directly or indirectly affect weight change such as diet, medication, food access and environment.
3. Collect data on participant height change over 6 months to calculate body mass index (BMI)

II. Background and Introduction

Prader-Willi syndrome (PWS) is a complex neurodevelopmental disorder resulting from disruption of an imprinted region of chromosome 15 (15q11.2-q13). PWS has an estimated incidence of 1:15,000-1:30,000 births worldwide, and equally affects males and females of all ethnicities. PWS

is characteristically associated with feeding difficulties and failure to thrive in infancy and early childhood, followed by the development of excessive eating (hyperphagia), intense food seeking behavior, and morbid obesity. Additional features of PWS include poor muscle tone and strength (hypotonia), hypogonadism, osteoporosis, scoliosis, infertility, delayed motor and language development, impaired cognition, sleep abnormalities, behavioral challenges including tantrums, obsessive compulsiveness and skin picking, and psychiatric illness in adulthood. The phenotype exhibits a broad spectrum of severity.

The incidence and natural history of several PWS symptoms are poorly defined. Gathering data on these is essential not only to understand the development and severity of each symptom without relying on anecdotal evidence, but also to appropriately direct therapeutic efforts and clinical trials.

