A copy of the completed consent form will be made available to all participants.

VII. Data Analysis and Reporting

The following analyses are planned

1. Trends in weight and BMI change over 6 months.
2. Description of factors that could affect weight and BMI in this group, including food access, change in living situation, physical activity and medication.

VIII. Facilities and Performance Sites

This study will use mobile health technology. Interested participants will sign an informed consent and provide a mobile phone number on which they are able to send and receive text messages. FPWR will assign each participant a unique, random, study-related ID, not linked to any identifying information (eg. fpwr2018_001). Only this unique ID will be used on the Mosio platform. The key to the IDs will only be available to researchers associated with this study. Once registered, participants will receive text messages and surveys at pre-determined intervals on their mobile phones (discussed above) and will respond directly via text. Mosio will store all data on a secure server and provide investigators a login to the site. Only study personnel will be able to access the data.

IX. Potential Benefits

There is no direct benefit to the patient from participating in the study. As mentioned above, real-world studies are essential in PWS to understand the natural progression of the disease. At the end of the study, participants will receive a personalized chart detailing their weight progression over the course of the study.

X. Potential Risks, Discomforts, Inconveniences, and Precautions

Participation in the study presents minimal risks to its participants. The greatest risk is loss of confidentiality of personal health information.

XI. Risk/Benefit Analysis:

This is a minimal risk study without direct benefits to the individual. There are no risks of physical harm associated with participation in the study. While every effort will be made to keep data confidential there is a potential risk of a breach of confidentiality of medical information and associated privacy of the participants. This risk will be minimized by storing data on a secure server. Only authorized study personnel will have access to the data.

XII. Privacy and Confidentiality:

Participants' privacy and confidentiality will be safeguarded by using modern database management techniques and informed consent. Only authorized study personnel will have access to the data.

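### The food-access survey question (item 2) is the only one of four change questions with no recall period, so its month-6 answer can repeat or net out a change from months 0-3

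*Protocol*

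**What the plan says.** Under Data to be collected (Protocol, section III), item 3 sets the timing: "At 3 months and 6 months participants will answer a survey". Four of its five questions ask about change, and three of these state their period:

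- Item 1, living situation: "Has there been any change in the living situation for the person with PWS in the last 3 months"
- Item 3, activity: "Has the activity level in the last 3 months increased/decreased/stayed the same for the person with PWS"
- Item 4, medication: "Has there been medication change in the last 3 months for the person with PWS"

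Item 2, on food access, states none: "To your knowledge has access to food at home or outside the home increased/decreased/stayed the same for the person with PWS".

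Item 5 asks for height and is not a change question. Weights are texted in "Once a week, every week, for 6 months".

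Food access has a stated role in the study. Objective 2 in section I reads "Study factors that could directly or indirectly affect weight change such as diet, medication, food access and environment", and the second analysis in section VII is a "Description of factors that could affect weight and BMI in this group, including food access" and other factors.

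**The concern.** A question about change needs a reference point. When the same question is put twice, the second answer can be used for the second interval only if the respondent knows to count from the first survey. Items 1, 3 and 4 secure this; item 2 leaves it to the respondent.

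Two errors can follow at month 6. A respondent whose access rose in months 0-3 and then held steady may report a rise again, so one change is recorded twice. A respondent whose access rose and then fell back may report no change, so the later fall is lost.

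With weekly weights, each survey answer could be set beside the weights of its own 3 months. For respondents with an earlier change, this cannot be done reliably with the month-6 food-access answer, although it can with the answers to the other three items.

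**Working it through.** **Step 1: compare the wording.**

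| Item | Topic | Answer format | Period stated |
|---|---|---|---|
| 1 | Living situation | yes/no | preceding 3 months |
| 2 | Food access | up / same / down | none |
| 3 | Activity | up / same / down | preceding 3 months |
| 4 | Medication | yes/no, with drug list | preceding 3 months |

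So 3 of 4 change questions state a period and 4 - 3 = 1 does not. Item 3 uses the same three-way scale as item 2 and does state the window, which suggests an oversight rather than a choice.

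**Step 2: look for the period elsewhere.** No lead-in sentence applies a window to the whole survey. The baseline survey in section III covers diagnosis by blood test, gender, age, growth hormone and weighing frequency. It has no food-access question, so change cannot be rebuilt from levels. Under section VIII, replies come directly by text, and no interviewer is described who could clarify the period.

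**Step 3: list what a month-6 answer can mean.** The inputs are the three answer options and the two survey times; no rates are assumed. Let c1 be the change in months 0-3 and c2 the change in months 3-6. Each takes a value in {-2, -1, 0, 1, 2}, so that opposite changes can differ in size.

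- Month-3 answer = sign(c1)
- Month-6 answer, reading A (since month 3) = sign(c2)
- Month-6 answer, reading B (since enrolment) = sign(c1 + c2)

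For each of the 3 x 3 = 9 answer pairs, the directions of c2 that fit under A or B are:

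| Month 3 | Month 6 | Possible direction in months 3-6 | Ambiguous? |
|---|---|---|---|
| same | up | up | no |
| same | same | same | no |
| same | down | down | no |
| up | down | down | no |
| down | up | up | no |
| up | same | same or down | yes |
| down | same | same or up | yes |
| up | up | up, same or down | yes |
| down | down | down, same or up | yes |

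Three cases under reading B show how this arises:

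- c1 = 1, c2 = 0: sign(1) = up, so the earlier rise is repeated.
- c1 = 1, c2 = -1: sign(0) = same, so the later fall is netted out.
- c1 = 2, c2 = -1: sign(1) = up, although access fell in months 3-6.

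Result: 4 of 9 pairs are ambiguous and 5 are not. All 4 have a change reported at month 3. If the month-3 answer is missing, c1 is unrestricted and each of the 3 month-6 answers fits any direction of c2.

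**Step 4: check from the side of true changes.** Let each period go up, same or down, with opposite changes of equal size. There are again 9 patterns. Readings A and B give different month-6 answers in 4 of them: 2 where an early change is followed by none (repeated) and 2 where it is reversed (netted out). They agree in the 3 patterns with no early change and the 2 with both changes in one direction. This counts true patterns, not answer pairs, so the shared total of 4 does not confirm the figure in step 3. It does confirm that the problem arises only after a change in months 0-3.

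**Step 5: apply the window.** With a 3-month window in item 2, the month-6 answer equals sign(c2) in all 9 patterns.

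**The case against.** The strongest reply is that the harm depends on an analysis the protocol does not plan. Section VII foresees trends over 6 months and a description of factors; it nowhere says that survey answers will be matched to weights 3 months at a time. A since-enrolment answer would serve the 6-month change. This stands as a limit on the weight of the point: period matching is a use the design allows, not one it announces. It does not remove the defect, because a since-enrolment answer helps only if it is known to be one. The month-3 answer shows who may be affected, not which reading they used.

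Second, item 2 sits between items that state the window, in a survey sent every 3 months, and many respondents may carry the window over. That is plausible. But the text does not say so, and a mixture of readings cannot be separated afterwards.

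Third, 4 of 9 counts logical possibilities and gives neither reading a weight. That is right; it should not be read as a proportion of participants.

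Fourth, a respondent might count from before enrolment, which the enumeration leaves out. This stands too: the month-3 answer has no stated reference point either, so the count may understate the ambiguity.

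Finally, the messages as sent may differ from the protocol's list, which is partly in shorthand. They cannot be seen here. The protocol nevertheless sets out the question, and it includes the window in the three items around it.

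**Conclusion.** The concern holds and is minor. Item 2 is the only one of the four change questions without a recall period. For respondents with a change in months 0-3, or with no month-3 answer, its month-6 answer does not reliably describe months 3-6. Respondents who report no change at month 3 are largely unaffected.

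The count of 4 ambiguous answer pairs in 9 rests on two readings being possible (since month 3 and since enrolment) and on the month-3 answer referring to months 0-3. The number of participants affected cannot be computed from the protocol.

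The point is worth raising despite its size because the question wording is fixed in the protocol, and an analysis plan cannot supply a reference period that respondents were never given.

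**What to change.** Add to survey item 2 the same last-3-months window that items 1, 3 and 4 carry, and use that wording at both month 3 and month 6. The two surveys then cover two separate intervals for all four change questions.

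The cost is one edit when the text messages are set up. Sample size, schedule and number of questions stay as they are. If the messages have already been programmed, the stored question text must be changed before it is sent; the protocol does not say whether that stage has been reached.

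### A participant who misses the month-3 survey but answers at month 6 has no record of living-situation, activity or medication changes in months 0-3, because the month-6 questions look back only 3 months

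*Protocol*

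**What the plan says.** Under Data to be collected, item 3, Section III of the protocol states: "At 3 months and 6 months participants will answer a survey". The same five questions serve both occasions. Three of them carry a fixed 3-month look-back:

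- Question 1, living situation: "Has there been any change in the living situation for the person with PWS in the last 3 months"
- Question 3, activity: "Has the activity level in the last 3 months increased/decreased/stayed the same for the person with PWS"
- Question 4, medication: "Has there been medication change in the last 3 months for the person with PWS? Y/N"

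Question 2, on food access, states no window: "To your knowledge has access to food at home or outside the home increased/decreased/stayed the same for the person with PWS".

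The other contacts are an enrolment survey, headed "Initial Survey at baseline only", and a weekly prompt to "send a text response with the participant's weight". Section VIII describes surveys sent at fixed intervals. It mentions no catch-up survey and no wording that depends on whether an earlier survey was answered.

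Section VII, item 1, plans weight and BMI trends over 6 months. Item 2 plans a "Description of factors that could affect weight and BMI in this group, including food access, change in living situation, physical activity and medication". Factors affecting weight are the second of the primary objectives in Section I.

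**The concern.** The outcome runs over 6 months, while each survey covers 3. A participant can text weights every week, overlook the month-3 survey and answer the month-6 survey. If a drug was stopped or the household moved in month 2, a truthful month-6 answer is no. That answer says nothing about months 0-3, yet it could easily be taken as covering the whole period.

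Missed surveys are foreseeable. The study is run remotely by text message, participants bear any message charges (Section XIII) and they receive no payment (Section XIV). At stake is the completeness of the factor data for objective 2 in people whose weight series may be complete. The information is lost at collection, so later analysis can only choose how to live with the gap.

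**Working it through.** The protocol gives no figure on this point (no missed-survey rate, no rate of change in any factor), so there is nothing to reproduce. The check has two parts.

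**1. Coverage, from the text alone**

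| Surveys answered | Months covered by questions 1, 3 and 4 |
|---|---|
| Month 3 and month 6 | 0-3 and 3-6: 6 of 6 |
| Month 6 only | 3-6: 3 of 6 |

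Could another contact fill months 0-3? The enrolment survey precedes those months. It lists growth hormone history but no general medication list, living situation or activity level, so a before-and-after comparison is not possible. The weekly text returns weight only. The gap therefore stays open.

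**2. Size, if the gap were read as no change**

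Inputs:
- N = 300, the target in Section V.c.
- m = share who miss month 3 but answer month 6: 15-25% (assumption).
- p = chance of a change in a given factor per quarter, independent between quarters: 20-40% (assumption).

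True share with any change in 6 months = 1 - (1 - p)²: 36% at p = 20%, 51% at 30%, 64% at 40%.

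Share of those changes that month 6 alone detects = p / [1 - (1 - p)²]: 0.20/0.36 = 56%, 0.30/0.51 = 59%, 0.40/0.64 = 63%.

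People without a month 0-3 record = N × m: 300 × 0.15 = 45 to 300 × 0.25 = 75.

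People wrongly counted unchanged = N × m × p × (1 - p), that is, a change in the first quarter and none in the second:

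| m | p | Wrongly unchanged |
|---|---|---|
| 15% | 20% | 300 × 0.15 × 0.20 × 0.80 = 7.2 |
| 15% | 40% | 300 × 0.15 × 0.40 × 0.60 = 10.8 |
| 25% | 20% | 300 × 0.25 × 0.20 × 0.80 = 12.0 |
| 25% | 40% | 300 × 0.25 × 0.40 × 0.60 = 18.0 |

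That is 2.4% to 6% of the 300 for each factor. A wider grid (m and p each from 10% to 30%) gives 2.7 to 18.9 people.

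Total counted unchanged, if everyone else answers both surveys = N × [(1 - m)(1 - p)² + m(1 - p)]:
- m = 15%, p = 20%: 300 × (0.85 × 0.64 + 0.15 × 0.80) = 199.2, of whom 7.2 (3.6%) are misplaced.
- m = 25%, p = 40%: 300 × (0.75 × 0.36 + 0.25 × 0.60) = 126, of whom 18 (14.3%) are misplaced.

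**The case against.** The strongest reply is that the design is sound as written. Two consecutive 3-month windows cover the 6 months without gap or overlap, and any two-wave survey loses its first window when the first wave is missed. How a missed survey is handled is commonly left to the analysis plan. This stands for the handling. It does not stand for the collection: the protocol fixes the wording of the questions, and an analysis plan cannot supply an answer that nobody asked for.

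A reader might infer that these participants will be counted as unchanged and that the factor comparisons will therefore be pulled toward no difference. The protocol supports neither step. Section VII plans a description, gives no rule for combining the two surveys and nowhere reads a missing survey as no. The direction of any bias is also open. Attenuation would follow if missing the survey were unrelated to weight change, but a move or an illness in the family could cause both.

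A reader might also take the 45-75 people without a month 0-3 record as the number misclassified. Most of them would be classified correctly; on the same assumptions 7-18 would not.

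Nor is a mismatch between outcome and exposure forced. Weights are collected weekly, so month-6 answers can be paired with weight change over months 3-6, which is exactly their window. This is a good reason to keep the 3-month wording for everyone. Finally, Section III gives the researchers access to the data during the study, so a missed survey would be visible at the time, but the protocol describes no procedure for following it up.

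**Conclusion.** The point holds in a limited form. For every participant who misses month 3 and answers month 6, changes in living situation, activity and medication in the first half of the study go unrecorded, and no other planned contact collects them. That follows from the text without assumptions. Food access is not part of the point, because its question has no stated window.

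The size cannot be determined from the protocol. The range of about 7-18 of 300 per factor depends on the assumed miss and change rates, on independence between quarters, on everyone who misses month 3 answering month 6, and on the gap being read as no change, which the protocol does not say. With a descriptive factor analysis, this is a minor improvement, worth making because it is cheap and has to be in place before the month-6 surveys go out.

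**What to change.** 1. **Section III, item 3.** Keep the 3-month questions unchanged for everyone at month 6. Where no month-3 survey is on file, add a Storyline branch that also asks questions 1, 3 and 4 for the participant's first 3 months in the study, with the drug list attached to question 4. Adding these items, rather than replacing the 3-month wording with a 6-month one, keeps the month 3-6 answers comparable across all participants. Question 2 has no look-back phrase to adapt and is left out of the branch.

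2. **Section VII, item 2.** State that a factor is related to 6-month weight change only where the answers cover all 6 months, and that otherwise the month-6 answers are paired with the weight change over months 3-6.

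Cost: one conditional branch and one sentence. Downside: longer and less accurate recall for the few who receive the added items. The branch does not help anyone who also misses month 6.
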